8.3.3 Chinese patient set

Patients in the Full Analysis Set who are recruited from a site located in mainland China of Chinese ethnicity.

8.4 Outcome measures for analyses

Independent Central Review of RECIST based assessments

The Independent Central Review of all radiological imaging data will be carried out using RECIST version 1.1. All radiological scans for all patients (including those at unscheduled visits, or outside visit windows) will be provided to the ICR. Prior radiotherapy reports for patients (at baseline) and information on biopsied lesions will also be provided to the ICR to allow the selection of appropriate target lesions. The imaging scans will be reviewed by two independent radiologists using RECIST 1.1 criteria and will be adjudicated if required. For each patient, the ICR will define the overall visit response data (CR, PR, SD, PD or NE) and the relevant scan dates for each time point (ie, for visits where response or progression is/is not identified). If a patient has had a tumour assessment which cannot be evaluated then the patient will be assigned a visit response of not evaluable (NE) (unless there is evidence of progression in which case the response will be assigned as PD). Endpoints (ORR, DoR, DCR, PFS) will be derived from the overall visit response date and the scan dates. ORR will only include patients whose response has been confirmed by a second scan at least 4 weeks after

the initial response. The endpoint of tumour shrinkage will be assessed from tumour size measurements based on the primary independent radiologist assessment.

Further details of the Independent Central Review will be documented in the Independent Review Charter.

Investigator RECIST based assessments

From the investigators review of the imaging scans, the RECIST tumour response data will be used to determine each subject's visit response according to RECIST version 1.1. It will also be used to determine the endpoints ORR, DoR, DCR and PFS from the overall visit response and scan dates.

At each visit, patients will be programmatically assigned a RECIST 1.1 visit response of CR, PR, SD or PD depending on the status of their disease compared with baseline and previous assessments. If a patient has had a tumour assessment which cannot be evaluated then the patient will be assigned a visit response of not evaluable (NE) (unless there is evidence of progression in which case the response will be assigned as PD).

Please refer to [Appendix C](#) for the definitions of CR, PR, SD and PD.

Overall Response Rate (ORR)

ORR rate is defined as the number (%) of subjects with measurable disease with at least one visit response of CR or PR that is confirmed at least 4 weeks later (according to ICR for the primary analysis). Data obtained up until progression, or last evaluable assessment in the absence of progression, will be included in the assessment of RR. However, any complete response or partial response which occurred after a further anticancer therapy was received will not be included in numerator of the ORR calculation.

In the case where a subject has two non-consecutive visit responses of PR, then, as long as the time between the 2 visits of PR is greater than 4 weeks and there is no PD between the PR visits, the subject will be defined as a responder. Similarly, if a subject has visit responses of CR, NE, CR, then, as long as the time between the 2 visits of CR is greater than 4 weeks, then a best response of CR will be assigned.

Duration of Response (DoR)

Duration of response will be defined as the time from the date of first documented response, (that is subsequently confirmed) until date of documented progression or death in the absence of disease progression, the end of response should coincide with the date of progression or death from any cause used for the PFS endpoint. The time of the initial response will be defined as the latest of the dates contributing towards the first visit response of PR or CR. If the response is not confirmed, it will not be included.

If a subject does not progress following a response, then their duration of response will use the PFS censoring time.

Disease control rate (DCR)

Disease control rate is defined as the percentage of patients who have a BoR of CR or PR or SD.

Tumour Shrinkage

Tumour shrinkage will be assessed using RECIST tumour response. The absolute change and percentage change from baseline in sum of tumour size at each assessment will be calculated. The best change in tumour size will include all assessments prior to progression or start of subsequent anti-cancer therapy.

Progression Free Survival (PFS)

PFS is defined as the time from enrolment until the date of objective disease progression or death (by any cause in the absence of progression) regardless of whether the patient withdraws from study therapy or receives another anti-cancer therapy prior to progression. Patients who have not progressed or died at the time of analysis will be censored at the time of the latest date of assessment from their last evaluable RECIST assessment.

However, if the patient progresses or dies after three or more missed RECIST assessments visits, the patient will be censored at the time of the latest evaluable RECIST assessment. If the patient has no evaluable visits or does not have baseline data they will be censored at 0 days unless they die within two visits of baseline.

The PFS time will always be derived based on scan/assessment dates not visit dates.

RECIST assessments/scans contributing towards a particular visit may be performed on different dates. The following rules will be applied

- Date of progression will be determined based on the earliest of the dates of the component that triggered the progression
- When censoring a patient for PFS the patient will be censored at the latest of the dates contributing to a particular overall visit assessment

Overall Survival

Overall survival is defined as the time from the date of first dose until death due to any cause. Any patient not known to have died at the time of analysis will be censored based on the last recorded date on which the patient was known to be alive.

Note: Patients should be contacted in the 2 weeks following the data cut-off for the final survival analyses to provide complete survival data

HRQoL & Symptoms

Patient reported outcomes will be assessed using the EORTC QLQ-C30 and QLQ LC13 questionnaires. The QLQ-C30 consists of 30 questions which can be combined to produce 5

functional scales (Physical, Role, Cognitive, Emotional, Social), 3 symptom scales (Fatigue, Pain, Nausea/vomiting), 5 individual items (dyspnoea, insomnia, appetite loss, constipation, diarrhoea) and a global measure of health status. The QLQ LC13 is a lung cancer specific module comprising 13 questions to assess lung cancer symptoms (cough, haemoptysis, dyspnoea and site-specific pain), treatment related side-effects (sore mouth, dysphagia, peripheral neuropathy and alopecia) and pain medication. With the exception of a multi-item scale for dyspnoea, all are single items.

An outcome variable consisting of a score from 0 to 100 will be derived for each of the symptom scales/symptom items, the functional scales and the global health status scale in the QLQ-C30 and for each of the symptom scales/items in the QLQ LC13 according to the EORTC QLQ-C30 Scoring Manual and EORTC QLQ LC13 instructions.

Higher scores on the global health status and functioning scales indicate better health status/function. Higher scores on the symptoms scales indicate greater symptom burden.

The primary PRO outcome measures will be patient-reported lung cancer symptoms assessed using the EORTC QLQ LC13, namely

- dyspnoea (multi-item scale based on 3 questions: were you short of breath when you rested; walked; climbed stairs)
- cough: 1 item (how much did you cough?)
- haemoptysis: 1 item (did you cough up blood?)
- pain: 3 individual items (Have you had pain in your chest; your arm or shoulder; other parts of your body?)

Definition of clinically meaningful changes

Changes in score compared to baseline will be evaluated. A minimum clinically meaningful change is defined as a change in the score from baseline of ≥ 5 for scales/items from the QLQ LC13 and ≥ 10 for scales/items from the QLQ-C30 (Obosa et al 1998).

For example, a clinically meaningful deterioration or worsening in chest pain (as assessed by QLQ LC13) is defined as an increase in the score from baseline of ≥ 5 . A clinically meaningful improvement in fatigue (as assessed by QLQ-C30) is defined as a decrease in the score from baseline of ≥ 10 .

At each post-baseline assessment, change in symptoms/functioning from baseline will be categorised as improved, stable or worsening as shown in [Table 8](#).

Table 8 Visit Response for HRQoL and disease-related symptoms

Score	Change from baseline	Visit Response
LC13 symptom scales/items	$\geq+5$	Worsened
	≤-5	Improved
	Otherwise	Stable
C30 symptom scales/items	$\geq+10$	Worsened
	≤-10	Improved
	Otherwise	Stable
C30 functional scales and Global health status	$\geq+10$	Improved
	≤-10	Worsened
	Otherwise	Stable

Time to symptom deterioration

For each of the symptoms scales/items in QLQ LC13, time to symptom deterioration will be defined as the time from enrolment until the date of first clinically meaningful symptom deterioration (an increase in the score from baseline of ≥ 5) or death (by any cause) in the absence of a clinically meaningful symptom deterioration, regardless of whether the patient withdraws from study therapy or receives another anticancer therapy prior to symptom deterioration. Death will be included as an event only if the death occurs within two visits of the last PRO assessment where the symptom change could be evaluated.

Patients whose symptoms (as measured by QLQ LC13) have not shown a clinically meaningful deterioration and who are alive at the time of the analysis will be censored at the time of their last PRO assessment where the symptom could be evaluated. Also, if symptoms progress after two or more missed PRO assessments or the patient dies after two or more missed PRO assessments, the patient will be censored at the time of the last PRO assessment where the symptom could be evaluated. If a patient has no evaluable assessments or does not have baseline data they will be censored at day 1. The population for analysis of time to symptom deterioration will include a subset of the FAS population who have baseline scores ≤ 95 .

Symptom Improvement Rate

The symptom improvement rate will be defined as the number (%) of patients with two assessments at least 18 days apart (ie, 21 days allowing a visit window of 3 days) which showed a clinically meaningful improvement (a decrease from baseline score > 5 for LC13 scales/items or > 10 for C30 scales/items) in that symptom from baseline. The denominator

will consist of a subset of the FAS population who have a baseline symptom score ≥ 5 (LC13 scales/items) or ≥ 10 (C30 scales/items).

Time from enrolment to second progression (PFS2) (exploratory)

Time from enrolment to second progression (PFS2) is defined as the time from the date of enrolment to the earliest date of the progression event subsequent to that used for the primary variable PFS or death. The date of second progression will be recorded by the Investigator and defined according to local standard clinical practice and may involve any of; objective radiological or symptomatic progression or death. Patients alive and for whom a second disease progression has not been observed should be censored at the last time known to be alive and without a second disease progression, ie, censored at the last progression assessment date if the patient has not had a second progression or death).

Time to second subsequent anti-cancer therapy or death is defined as the time from the date of enrolment to the earlier of the date of second subsequent anti-cancer therapy start date, or death date. Any patient not known to have had a further second subsequent therapy or death will be censored at the last known time to have not received second subsequent chemotherapy.

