Echocardiogram/MUG A	X		← every 12 weeks(±1 week) relative to first dose →										5.2.5
Plasma sample for ctDNA ^g	X ⁱ	X	X	X	X	X	X		← every 6 weeks in line with RECIST assessments ^j →			4.3.3 & 5.6.2	
Optional genetic consent and sample	X ^k												5.5
Optional CSF sample					X (once only) ^l								5.4.1

Table 1 Study Plan - Prior to 24 months post LSFD

Visit	Screening	Treatment Period (further treatment cycles as per Cycle 7)							Treatment Discontinuation	Follow-up Period			For details see Protocol Section
	1	2	3	4	5	6	7-9	10+		28-day follow-up	Progression follow-up	Survival follow-up	
Cycle ^a / Day		C1 D1	C1 D8	C1 D15	C2 D1	C3 D1	C4-6 D1	C7 ^b +D1	NA	NA	NA	NA	
Day	-28 to 1	1	8	15	22	43	64-106	127+	NA	NA	NA	NA	
Window (days) ^z	NA	0	±2	±2	±7	±7	±7	±7	0	±7	±7	±7	SECTION:
Tumour assessments (RECIST v1.1) ^m	X ^v	every 6 weeks(±1 week) relative to first dose until disease progression 										4.2 & 5.1.1	
EORTC QLQ-C30 and EQ-5D-5L (by electronic device)		X ^g	every 6 weeks(±1 week) relative to first dose 					X		X ⁿ	X ⁿ	5.3.2.1 & 5.3.2.2	
EORTC QLQ LC13 (by electronic device)		X ^g	Weekly(±2days) relative to first dose 		every 3 weeks(±3 days) relative to first dose 			X		X ^o	X ^o	5.3.2.1	
PRO-CTCAE (by electronic device) ^p		X ^g	weekly(±2 days) for first 18 weeks of treatment 				X ^q	X		X ^o	X ^o	5.3.2.3	
Healthcare Resource Use												5.3.2.5	
Dispense study medication		X			X	X	X	X ^b					3.3 & 7.2

Table 1 Study Plan - Prior to 24 months post LSFD

Visit	Screening	Treatment Period (further treatment cycles as per Cycle 7)							Treatment Discontinuation	Follow-up Period			For details see Protocol Section
	1	2	3	4	5	6	7-9	10+		28-day follow-up	Progression follow-up	Survival follow-up	
Cycle ^a / Day		C1 D1	C1 D8	C1 D15	C2 D1	C3 D1	C4-6 D1	C7 ^b +D1	NA	NA	NA	NA	
Day	-28 to 1	1	8	15	22	43	64-106	127+	NA	NA	NA	NA	
Window (days) ^z	NA	0	±2	±2	±7	±7	±7	±7	0	±7	±7	±7	SECTION:
Dose with AZD9291		← Daily dosing →											7.2
Concomitant medication & procedures		← →											7.7
Adverse events ^w		← →									X ^t	X ^t	6.3 & 6.4
Survival Status												X ^s	4.3.4
Anti-cancer treatment	X										X	X ^s	4.3.3, 4.3.4
Subsequent response /progression data												X ^t	5.8

^a A cycle is defined as 21-day treatment period.

^b Visit schedule changes after Cycle 7 Day 1 from every 21 days (3 weeks) to every 42 days (6 weeks).

^c Consent may be taken prior to 28-day window if required,

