^d Taken following progression on the latest line of therapy. The collection of this tumour tissue sample for central mutation analysis is not included in the 28-day screening period.

^e The optional second tumour tissue sample can be taken as part of the same procedure as the mandatory screening biopsy for mutation analysis.

^f Archival tumour sample only to be submitted after T790M positive status confirmed by central testing. Not required for T790M negative patients.

^g To be completed pre-dose.

^h If screening assessments are not done at Visit 2, but have been done at Visit 1 and have been performed within 14 days window prior to starting study treatment, with no change in condition and no clinical indication to do so, they do not have to be repeated on Visit 2 if subject's condition has not changed. (except for fasting glucose).

ⁱ To be taken at the same time as the screening biopsy is taken or prior to mutation screening. All plasma samples are required by AstraZeneca, regardless of the outcome of the mutation screening.

^j Collect every 6 weeks up to and including progression (corresponding with the RECIST assessments – and continuing after treatment discontinuation in absence of disease progression).

^k If for any reason the sample is not drawn prior to first dose it may be taken at any visit until the last study visit.

^l To be obtained at one time point at any time from Cycle 2 Day 1 onwards

^m If only one measurable lesion exists, it is acceptable to be used as long as it has not been previously irradiated, and baseline tumour assessment scans are done at least 14 days after the screening biopsy is performed.

ⁿ Assess every 6 weeks relative to first dose until end of study (including survival follow-up period) and at the time of progression.

^o Assess every 3 weeks relative to first dose until end of study (including survival follow-up period) and at the time of progression.

^p PRO-CTCAE will only be administered in those countries where a linguistically validated version exists.

^q Assessed at Cycle 7 Day 1 then every 3 weeks relative to first dose thereafter until end of study (including survival follow-up period) and at the time of progression.

^r Following AZD9291 discontinuation, SAEs considered related to study procedures should continue as outlined in Table 6.

^s Survival status including anti-cancer treatment to be performed every 6 weeks (relative to first dose) following disease progression or withdrawal from treatment.

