EORTC QLQ-C30 and EQ-5D-5L (by electronic device)	← X (every 6 weeks until end of study and at the time of progression) relative to first dose →					5.3.2.1 & 5.3.2.2
EORTC QLQ LC13 (by electronic device)	← X (every 3 weeks until end of study and at the time of progression) relative to first dose →					5.3.2.1
PRO-CTCAE (by electronic device)	← X (every 3 weeks until end of study and at the time of progression) relative to first dose →					5.3.2.3
Healthcare Resource Use	← →					5.3.2.5
Dispense study medication	X					3.3 & 7.2
Dose with AZD9291	Daily dosing					7.2
Concomitant medication & procedures	← →					7.7

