5.3.2.4 Administration of electronic PROs

Patients will complete the PRO assessments using a handheld electronic device (ePRO). The following best practise guidelines should be followed when collecting PRO data via an electronic device:

- Explain the value and relevance of participation to patients that we are asking these questions because we are interested in hearing directly from them how they feel. The research nurse or appointed site staff should also stress that the information is confidential. Therefore, if the patient has any medical problems he/she should discuss them with the doctor or research nurse separately from the ePRO assessment.
- Remind patients that there are no right or wrong answers, avoid bias by not clarifying items.
- Train the patient on how to use the ePRO device using the materials and training provided by the ePRO vendor. Also provide guidance on whom to call if there are problems with the device.

Monitor compliance: minimizing missing data is a key aspect of study success. Compliance must be checked at each study visit and should be checked more frequently to identify problems early. If compliance drops below 85% a check-in call from the site to ask the patient if he/she has any difficulties is highly recommended.

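### Time to symptom deterioration counts missed forms, not days, so a worsening seen after a 21-day gap is censored while LC13 is weekly, yet one seen after 42 days counts once LC13 is 3-weekly

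*Protocol*

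**What the plan says.** Protocol Section 8.4 defines the endpoint item by item: "For each of the symptoms scales/items in QLQ LC13, time to symptom deterioration will be defined as the time from enrolment" to the first increase of at least 5 points from baseline, or death. It then adds a gap rule: "if symptoms progress after two or more missed PRO assessments", or the patient dies after the same number of missed assessments, "the patient will be censored at the time of the last PRO assessment where the symptom could be evaluated". A separate sentence counts a death as an event only if it falls within two visits of the last evaluable PRO form. Neither rule gives a length of time.

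The LC13 row of Table 1 (Section 4) has two frequencies: first "Weekly(±2days) relative to first dose", then "every 3 weeks(±3 days) relative to first dose". Footnote o of Table 1 continues the slower frequency: "Assess every 3 weeks relative to first dose until end of study (including survival follow-up period) and at the time of progression". Table 2, which covers the period after 24 months, agrees: "X (every 3 weeks until end of study and at the time of progression) relative to first dose". Sections 4.3.3 and 4.3.4 also give 3-weekly collection during follow-up.

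Section 5.3.2.4 gives one completion level: "If compliance drops below 85% a check-in call from the site" is recommended. Section 8.7.2 presents the endpoint as a Kaplan-Meier plot, a median and the proportions free of deterioration at 3, 6, 12 and 24 months.

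**The concern.** A gap rule is there to avoid dating an event when the patient has been unobserved for too long. How long is too long should be a length of time. Here it is a number of forms, and the time between forms triples during the study. The rule is therefore strictest in the first weeks, where observation is densest, and it discards worsenings seen after a gap that is full compliance later on.

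The censoring also depends on the outcome. Take a patient who completes baseline, misses weeks 1 and 2 and returns at week 3. If the score is unchanged, the patient remains in the risk set. If it is worse, the patient is censored back at baseline and the event is lost. Events are removed while comparable non-events are kept, so the curve moves in one direction, upward. At stake are the early part of the LC13 curves and the 3-month proportion, for the measures that Section 8.4 calls the primary PRO outcomes.

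**Working it through.** **Inputs from the protocol.** Weekly phase: interval 7 days, window 2 days. Later phase: interval 21 days, window 3 days (Table 1). Censoring trigger: two missed forms (Section 8.4), read here as the run of missed forms just before the form that shows the worsening. Completion alert level: 85%, that is 15% missed (Section 5.3.2.4).

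**Step 1: the gap implied by the rule.** Gap = (missed forms + 1) × interval, give or take 2 × window, since both end forms can shift.

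| Phase | Missed forms | Gap in days | Range with windows | A worsening then is |
|---|---|---|---|---|
| Weekly | 1 | 2 × 7 = 14 | 10-18 | an event |
| Weekly | 2 | 3 × 7 = 21 | 17-25 | censored |
| 3-weekly | 0 | 1 × 21 = 21 | 15-27 | an event |
| 3-weekly | 1 | 2 × 21 = 42 | 36-48 | an event |
| 3-weekly | 2 | 3 × 21 = 63 | 57-69 | censored |

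The same 21-day gap is censored in one phase and is full compliance in the other. To reach the 42-day gap accepted later, a patient in the weekly phase would have to miss 42/7 − 1 = 5 forms; to reach the 63-day gap, 63/7 − 1 = 8.

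**Step 2: how often such a run occurs.** With 15% of forms missed independently, the chance of at least one run of two missed weekly forms is 4% over 3 forms, 10% over 6, 15% over 9 and 29% over 18. The range is needed because the week of the switch cannot be read from the extracted Table 1. Only patients whose worsening is first seen straight after such a run lose an event.

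**Step 3: effect on the estimate.** Simulation of 200,000 patients. Assumptions: forms at weeks 1-6 and then every 3 weeks; a 5-10% chance of worsening per form; missingness unrelated to health, either independent or moderately clustered. At 85% completion, moderate clustering means that a missed form is followed by another with probability 0.4. The present rule is compared with a 48-day rule. Worsening is modelled in two ways: arising afresh at each form, or persisting once begun.

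| Completion | Worsening | Week 1-6 deteriorations lost | 12-week estimate too high by |
|---|---|---|---|
| 85% | fresh at each form | 1.6-3.2% | 0.3-0.9 points |
| 85% | persists | 4-9% | 1.0-2.4 points |
| 70% | fresh at each form | 6-8% | 1.1-2.0 points |
| 70% | persists | 15-20% | 3.4-5.9 points |

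The 70% rows are a sensitivity range; the protocol gives no such figure.

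**Step 4: in patients.** Number lost = 175 × share of patients whose first observed worsening is in weeks 1-6 × share of those lost. The lowest 85% case is 175 × 0.231 × 0.016 ≈ 0.6 patients per symptom. The highest is 175 × 0.454 × 0.086 ≈ 7.

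**The case against.** The strongest objection is size. At 85% completion more than nine in ten early deteriorations are kept, and the curve moves by a point or two at most. The endpoint is a descriptive summary of a secondary objective in a single-arm trial, with no comparator, test or decision rule; the trial's primary endpoint is ORR. All of that stands and limits the importance of the point.

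Second, 85% is a level that prompts a call about one patient, not an expected average, and the 6-week weekly phase is assumed. That stands too. It affects the magnitude but not Step 1.

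Third, the weeks 1 and 2 example falls on the Cycle 1 Day 8 and Day 15 clinic visits, where compliance has to be checked, so that gap is less likely than most. This stands for that example. Weeks 4 and 5 have no scheduled clinic visit, so if the weekly phase runs that far a gap there has no such protection. The discarded worsening would still appear in the by-timepoint summaries of Section 8.7.2, but not in the time-to-event estimate.

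Fourth, counting missed assessments is a convention that the PFS rule also uses, and a tolerance scaled to assessment frequency can be defended. But RECIST imaging is 6-weekly throughout the period in which it is collected, so a count corresponds to one length of time there; for LC13 it does not. The next endpoint in Section 8.4, symptom improvement, sets its spacing in days. An SAP could define the gap in days, but the protocol has already fixed it as a count of forms, so such an SAP would depart from the protocol.

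A reader might also infer that sicker patients skip early forms and that the bias is therefore substantial. The documents say nothing about who misses forms, so that inference is unsupported. It is also not needed, because the upward shift arises with missingness unrelated to health.

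**Conclusion.** The inconsistency is real and exact: a worsening after 21 days is discarded early, one after 42 days counts later, and nothing in the protocol reconciles the two. The direction is known, since the present rule can only raise the deterioration-free curve relative to a time-based rule. The size is small: about 2-9% of early deteriorations and up to about 2 points on the 12-week estimate, given a 6-week weekly phase, 85% completion and 5-10% worsening per form. It grows if completion is poorer.

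The documents do not support reading this as a general loss of early deteriorations or as a threat to the trial's main conclusions. It is a modest defect in a descriptive secondary endpoint, worth correcting because the correction is cheap.

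**What to change.** In Section 8.4, replace the count of missed PRO assessments with a time limit for the whole endpoint. Censor a deterioration or a death at the last evaluable LC13 only if more than 48 days have passed since that form. The limit is two 3-week intervals plus a 3-day window at each end: 2 × 21 + 2 × 3 = 48. It separates one missed 3-weekly form (36-48 days) from two (57-69 days), so the present deterioration rule is unchanged in the 3-weekly phase.

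State the two-visit death rule with the same 48-day limit. Otherwise, after two missed weekly forms, a worsening would count but a death would be censored. The visit count is also unclear here, because clinic visits move to every 42 days after Cycle 7 Day 1 while LC13 stays at 21.

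The cost is a short wording change and one programming condition, with no new data. There are three consequences to accept:

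- In a 6-week weekly phase the longest possible gap is 42 days (44 with the 2-day window), so the rule would in practice never censor a worsening there.
- A few early events would be dated up to 48 days after the last form, as later ones already can be.
- For deaths in the 3-weekly phase, the second missed form falls due 36-48 days after the last one, so a few deaths near the limit may be classified differently from now.
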